1. CLINICAL PROTOCOL

1.1 Background

Cochlear implants have been used for decades to improve hearing via direct stimulation of first order auditory neurons in the cochlea. CIs enhance hearing in the vast majority of users with either pre- and post-lingually deafness, and many CI recipients demonstrate open set word understanding. The auditory brainstem implant or ABI was first placed in a human adult patient 1979 in Los Angeles and is indicated for patients who are deaf and cannot receive a CI. The ABI bypasses the damaged or absent auditory nerve to stimulate the second-order neurons in the brainstem through placement of a surface electrode array on the cochlear nucleus (CN). Over 1000 pediatric and adult ABIs have been placed worldwide. Because ABI stimulation occurs further along the auditory pathway with activation of higher order neurons, this technology can take advantage of pathways that remain intact in patients with cochlear and retrocochlear pathology.

Our study aims to determine the efficacy of ABI in individuals with severe or profound hearing loss due to cochlear or retrocochlear anomalies distinct from NF2. In particular, base of skull/temporal bone fractures leading to VIIIth nerve avulsion, cochlear nerve agenesis or deficiency, cochlear aplasia, cochlear ossification, and auditory neuropathy prevent the faithful transmission of auditory information from the cochleae to the brainstem. These individuals do not benefit from hearing aids or CIs; however, there are cases where patients with these non-NF2 etiologies have greatly benefited from ABI placement.

The IDE Supplement for design change replaces the receiver / stimulator from the Nucleus ABI24M with the Nucleus ABI541. Both ABI devices feature a multichannel electrode lead that terminates in twenty-one, 0.7 mm platinum disk-electrodes. The 21

platinum contacts are arranged on the surface of a silicone rubber pad in three rows of seven contacts and are surgically placed on the surface of the brainstem; specifically, on the surface of the cochlear nucleus.

1.2 Rationale

The data supporting the clinical safety and efficacy of the Nucleus ABI24 in NF2 patients were provided to the FDA in March 2000, and later approved on July 21, 2000 unanimously for use by individuals with NF2. Other FDA criteria for ABI include age of 12 years or older, high motivation to participate in the rehabilitation process and appropriate patient expectations. Cochlear Americas subsequently received approval from the FDA in October 2000 (PMA No. P000015) for use of the ABI24 system in NF2 patients.

This proposed study aims to test the safety and clinical efficacy of the previously approved Nucleus ABI24 and new ABI541 systems in a small cohort of non-NF2 deaf patients, who are not candidates for or who have not benefited from CIs. Based on studies in Europe as well as at the University of North Carolina and House Ear Institute (University of California, Los Angeles), ABI placement in non-NF2 subjects leads to significant improvement in sound and speech recognitions skills (Colletti et al., 2001, Colletti et al., 2002, Colletti et al., 2004a, b, c, Colletti et al., 2005, Sanna et al., 2006, Sennaroglu et al., 2011, Grayeli et al, 2007). Enhanced auditory perception in non-NF2 patients with ABIs appears superior to ABI outcomes in NF2 patients, in part because the auditory pathways of non-NF2 patients have not been compromised. Indeed, based on these findings, several centers throughout the U.S. are now placing ABIs in non-NF2 patients as an off-label, non-FDA approved use of the Nucleus ABI24 system. We hope to complete a formal study examining the efficacy and safety of ABIs in non-NF2 patients. In particular, we will perform pre-operative, intra-operative, and post-operative physiological, psychophysical, and speech testing of non-NF2 patients who have undergone ABI surgery and thereby determine outcomes of ABI placement in this unique population of patients.

The Nucleus ABI24 has already been used safely and effectively in nontumor patients in prior studies completed in Europe and internationally (Colletti et al., 2010, Sennaroglu et al., 2009, Choi et al., 2011, Colletti et al., 2009). At MEEI, we are currently using the ABI24 system in NF2 patients safely and with good clinical outcomes, and importantly, the procedures for placement, activation, and management of the ABI24 device are identical in NF2 patients and the proposed cohort of non-NF2 patients. Thus, use of the ABI24 system in non-NF2 patients as part of our study will be safe and effective, even though this is an off-label use. Given that the stimulation methodology and electrode technology are unchanged in the new ABI541, the stimulation delivered by the ABI541 should be identical to that delivered by the ABI24M and should have the identical risks to the ABI24.

Subjects in our study will meet the basic criteria of being 18 years or older, medically and psychologically suitable ABI surgery candidates, up to date on meningitis vaccinations, and able to comply with study requirements. In addition, subjects will be chosen on the basis of cochlear or retrocochlear anomaly/pathology that interferes with transmission of auditory information from the cochleae to the brainstem, resulting in severe to profound bilateral deafness or conditions that cannot be treated otherwise, with conventional hearing aids or cochlear implants. If CI were previously used, subjects will have had a failed response, defined as $\leq 30\%$ speech recognition and patient perception of inadequate benefit to continue using the device. Anticipated subjects include patients with bilaterally ossified cochleae (including a subgroup of recipients with failed response to previous CI), bilateral cochlear malformations leading to poor CI outcomes, bilateral temporal bone fractures, where the VIIIth cranial nerves have been disrupted, bilateral cochlear nerve agenesis, and those that are no CI candidates.

2. STUDY OBJECTIVES

2.1 Primary Objective

The primary objective of this study is to better understand whether ABIs in non-NF2 patients may enhance hearing and sound detection in patients with severe to profound hearing loss. Our study will address several specific aims including:

Aim 1: Identification of ABI outcomes in non-NF2 patients - We will be testing the hypothesis that individuals with a range of conditions distinct from NF2 may benefit from the placement of an ABI. In particular, we will be exploring the performance of these patients in a battery of physiological, psychophysical, and speech-based tests including the Early Speech Perception Test, closed-set word recognition, and open-set word recognition with and without lip-reading cues. The performance of these patients will be compared to NF2 patients to better understand whether there are differences in these two patient groups.

Aim 2: Characterization of ABI parameters in non-NF2 patients - We will examine differences in electrode placement, stimulation selectivity, and modulation detection to test the hypothesis that non-NF2 patients have unique physiological ABI parameters compared to NF2 ABI patients. In addition, we will take advantage of intraoperative electrically evoked auditory brainstem responses to determine whether waves evoked during electrode placement intraoperatively are associated with auditory sensations postoperatively in non-NF2 patients.

Aim 3: Determination of ABI safety in non-NF2 patients - By carefully tracking post-operative outcomes following ABI placement in non-NF2 patients, we will test whether these patients have reduced major and minor complications compared to NF2 ABI patients.

2.2 Secondary Objective(s)

There are no secondary objectives of the proposed study.

3. STUDY DESIGN

3.1 Study Design Description

The study of the Nucleus ABI24 and ABI541 in non-NF2 patient will be conducted as a repeated-measure, single subject experiment with up to fifteen replications (goal of ten subjects, with 15 initially recruited to account for withdrawal or termination). A single subject research design in which each subject will serve as his or her own control will accommodate the heterogeneity of the subjects' background that is well known to influence auditory prosthesis outcomes and measures. Post-operative evaluations will be conducted at initial device activation, and three, six, and twelve months post-activation. Because the presence of absence of an ABI is easily recognized from visual inspection, blinding and masking procedures will not be utilized as part of the study design. The safety of the implant will be determined by monitoring major and minor complications in the cohort of study participants.

Pre-operative baseline measures will be obtained, including standard audiologic testing as described below.

Candidates that are suitable for surgery will undergo placement of an ABI. This surgery will utilize a translabyrinthine or retrosigmoid approach, depending on the anatomical and patient specific factors, to obtain access to the auditory nucleus of the brainstem. The electrode array of the ABI will then be placed and tested intra-operatively. After confirmation of optimal electrode array placement, the receiver will be implanted within the temporal bone posterior to the pinna. The patients overlying subcutaneous tissue and skin will then be closed and covered with dressings using standard surgical techniques.

Following surgical implantation of the Nucleus ~~ABI24~~ ABI541 and 4-12 weeks of healing, the device will be activated and auditory performance will be assessed as follows: at the time of activation and at three, six, and twelve months post-activation. Subjects will be evaluated with the prior approved Nucleus ~~ABI24~~ ABI541 speech processor programmed with an approved sound processing algorithm. Post-operative auditory function will be tested with a battery of psychophysical, speech perception, and lip-reading enhancement measurements.

The detailed list of post-operative assessments includes:

Initial Activation

Approximately 4-12 weeks post-operatively, subjects will be fitted with an approved Nucleus Sound Processor and initial stimulation will take place. The following procedures will occur at this visit:

- Modified Hearing Handicap Inventory, Dizziness Handicap Inventory, and Quality of Life (SF-36) questionnaires will be administered (see attached)
- Detection measures
- Speech perception and lip-reading enhancement measures
- Psychophysical measures
- Safety measures

Three, Six, and Twelve Months, and Biannual Post-activation Visits (for five years following ABI surgery):

The following procedures will occur at all these visits unless otherwise specified:

- Modified Hearing Handicap Inventory, Dizziness Handicap Inventory, and Quality of Life (SF-36) questionnaires will be administered (see attached)
- Detection measures at each post-activation interval

- Speech perception and lip-reading enhancement measures at each post-activation interval
- Psychophysical measures at each post-activation interval
- Safety measures at each post-activation interval

3.2 Allocation to Treatment

Because our study is a repeated-measure, single subject experimental design with up to fifteen replications, there is no proposed plan or procedure for allocating study participants to various cohorts of arms of the proposed clinical investigation.

4. SUBJECT SELECTION

4.1 Subject Inclusion Criteria

- 18 years of age or older
- English as the primary language
- Medically and psychologically suitable
- Willing to receive/have received meningitis vaccinations
- Able to comply with study requirements, including travel to the investigational site
- Cochlear or retrocochlear anomaly/pathology that interferes with transmission of auditory information from the cochleae to the brainstem, resulting in severe to profound bilateral deafness (thresholds of 90 dB or worse in both ears on pure tone audiometry and speech recognition scores \leq 30% in both ears)
 - Conditions causing deafness that cannot be otherwise treated with conventional hearing aids or cochlear implants. If CI were previously used, subjects will have had a failed response, defined as \leq 30% speech recognition and patient perception of inadequate benefit to continue using the device.
 - Expected subjects include those with:

- Bilaterally ossified cochleae (including a subgroup of recipients with failed response to previous CI)
- Bilateral cochlear malformations leading to poor CI outcomes
- Bilateral temporal bone fractures, where the VIIIth cranial nerves have been disrupted
- Bilateral cochlear nerve agenesis
- Not a CI candidate

4.2 Subject Exclusion Criteria

- Anomalies/pathology involving the brainstem or cortex
- Retrocochlear pathology resulting from NF2 or other types of cranial nerve or brainstem neoplasms or malignancies
- Co-existing medical conditions that require irradiation of the brainstem or auditory cortex
- Medical or psychological conditions that serve as contraindication to surgery
- Additional handicaps that would prevent or limit participation in evaluations
- Unrealistic patient or family expectations regarding the benefits, risks, and limitations inherent to the procedure and the prosthetic device
- Pregnant women

5. STUDY DRUG(S)/DEVICE(S)

5.1 Study Drug/Device Information

The Nucleus ABI24 system consists of a receiver/stimulator, a pocket sized speech processor worn on the body, and a microphone/headset. During surgery, the receiver/stimulator is implanted behind the ear. A wire leads from the receiver/stimulator to a series of 21 electrodes that are implanted in the auditory center of the brainstem, called the cochlear nucleus. The speech processor and microphone/headset pick up sound and transduce it into electrical impulses that are sent to the implanted receiver/stimulator. The impulse travels down the wire to the electrodes, which electrically stimulates the area that normally receives signaling from neurons of the ear.

The Nucleus ABI24 system is marketed under the brand name of Cochlear Nucleus 24 Multichannel Auditory Brainstem Implant and manufactured by Cochlear Americas (Engelwood, Colorado). In October 2000, the FDA approved use of the ABI24 system device in NF2 patients (PMA No. P000015).

Cochlear has developed a replacement for the ABI24M that uses the same electrode array as the existing ABI24M, but incorporates a more recent receiver/stimulator assembly. This device is referred to by Cochlear as the ABI541. The ABI541 is derived entirely from previous and existing approved products. The ABI541 uses the latest 500 series implanted receiver-stimulator, as is used in the current CI512 cochlear implant (approved in P970051/S116). This provides a slimmer electronics package for a reduced profile on the head and increased impact resistance in comparison to the ABI24M. The active electrode array is the same as used in the previously approved ABI24M.

5.2 Study Drug/Device Compliance/Adherence

Because the ~~ABI24 system~~ is an implanted device, there are few concerns regarding compliance and adherence compared to most typical clinical trials. Our study is

designed as a repeated-measure, single subject experiment, and thus, each participant will serve as his or her own control. Throughout the study, we will confirm that subjects have been using the device through routine clinical follow-up and questionnaires at each appointment. Both qualitative and quantitative measures will be obtained to determine if subjects are benefiting from the ABI24 system, and the individual activation parameters at each visit will be compared to the prior visit to ensure that settings on the device have not been altered or changed between visits.

Although we anticipate that the vast majority of subjects will derive a safe and substantial clinical benefit from use of the ABI24 system, if a given subject is non-compliant or non-adherent with use of the ABI24 system or external sound processor, then we will collect a final set of qualitative and quantitative measures and simply follow their outcomes through routine clinical exams. This approach will allow for monitoring of any adverse safety or health concerns that may arise. Thus, no subjects in our study will be formally withdrawn for non-compliance or non-adherence and all study participants will be followed for five years after ABI surgery. If a subject chooses to withdraw from the study, they will be replaced by new study participants recruited from the clinic.

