7. STUDY PROCEDURES

7.1 Screening Procedures

After confirming that potential study participants meet basic demographic inclusion criteria, patients will be evaluated by a trained Otologist at MEEI. A detailed history will be obtained and physical exam will be completed. Subjects will also be evaluated for baseline qualitative measures using questionnaires and quantitative

measures using audiologic testing. In particular, audiometric threshold testing and Auditory Evoked Potential testing will be completed to confirm acoustic auditory status. These parameters will be compared to inclusion criteria to determine if a subject meets all inclusion criteria and represents a viable candidate for ABI surgery.

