7.2 Enrollment/Baseline Procedures

All baseline procedures will be completed at the time of screening. This includes qualitative measurement using the Modified Hearing Handicap Inventory, Dizziness Handicap Inventory, and Quality of Life (SF-36) questionnaires as well as audiologic tests such as standard audiometric threshold and Auditory Evoked Potential testing.

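### The rule in 5.2 for subjects who stop using the implant most naturally ends their HHI, DHI and SF-36 before the five-year endpoint, although they stay enrolled.

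*Combined protocol and SAP*

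**What the plan says.** Section 5.2 (Study Drug/Device Compliance/Adherence) covers a subject who is non-compliant or non-adherent with the implant or the external sound processor: "then we will collect a final set of qualitative and quantitative measures and simply follow their outcomes through routine clinical exams". It adds that "no subjects in our study will be formally withdrawn for non-compliance or non-adherence" and that "all study participants will be followed for five years after ABI surgery". The reason it gives for this approach is that safety and health concerns can still be monitored.

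The general schedule is in 3.1. It lists HHI, DHI and SF-36 with the detection, speech, psychophysical and safety measures at three, six and twelve months and then biannually to five years, under the lead-in "The following procedures will occur at all these visits unless otherwise specified". Section 7.5 gives the same visit pattern.

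Two baseline sections show what qualitative means here. Section 7.1 speaks of "baseline qualitative measures using questionnaires", and 7.2 says of the baseline procedures: "This includes qualitative measurement using the Modified Hearing Handicap Inventory, Dizziness Handicap Inventory, and Quality of Life (SF-36) questionnaires".

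Section 8.2 numbers nine primary dependent measures. The three questionnaires are items 7 to 9, and all measures are compared with the subject's pre-operative baseline. Section 10.1 places the primary endpoint at five years after surgery. Section 10.4 analyses whatever data were obtained from all participants. On size, 3.1 states a "goal of ten subjects, with 15 initially recruited to account for withdrawal or termination".

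**The concern.** A subject who stops using an auditory implant is unlikely to be a random member of the cohort. The protocol makes the link itself: the inclusion criteria in 4.1 define failure of an earlier cochlear implant partly by the patient's view that the benefit was too small to go on using it. If questionnaires stop when use stops, the five-year values go missing for a reason plausibly connected with the outcome. The plan itself would cause the gap, in subjects who are still enrolled and still being seen.

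Two things are at stake. First, 8.2 and 10.5 evaluate each subject against his or her own baseline, and for a non-user that comparison would not exist at five years for the three questionnaires. Second, any summary of questionnaire results at late visits would describe mainly continuing users, in a cohort where each subject carries considerable weight.

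**Working it through.** The plan gives no figure on this point to reproduce: there is no non-use rate, no dropout rate and no effect size. The check is therefore a reading of the sections together, followed by counts.

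**1. What stops.** Section 5.2 collects a last set of qualitative and quantitative measures and then relies on routine clinical exams. Sections 7.1 and 7.2 tie qualitative to HHI, DHI and SF-36. Section 14.2 draws a similar line: if the study is discontinued, audiologic and safety measures go on as routine follow-up but the subjective questionnaires do not. That passage concerns closing the study, not one subject's non-use, so it supports the reading only by analogy. No section says that questionnaires continue for a non-user after the last set.

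**2. What need not stop.** Section 7.4 treats audiologic testing as standard of care, and 14.2 treats audiologic and safety measures as routine. The clear loss is therefore items 7 to 9 of 8.2, that is 3 of 9 measures.

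**3. Weight of one non-user.** 1/15 = 6.7%; 1/10 = 10%.

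**4. Questionnaire visits lost per non-user.** Non-adherence is not defined, so the time of the last set is an assumption. Biannual can mean six-monthly or two-yearly. Two totals arise under each reading because 3.1 counts visits from activation (4 to 12 weeks after surgery) while the five years run from surgery, so a month-60 visit may or may not fall inside the period.

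- Six-monthly: months 0, 3, 6, 12, then every 6 months to 54 (11 visits) or to 60 (12 visits).
- Two-yearly: months 0, 3, 6, 12, 36 (5 visits), or with 60 (6 visits).

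| Last set at | Six-monthly | Two-yearly |
|---|---|---|
| Month 3 | 9 of 11 or 10 of 12 | 3 of 5 or 4 of 6 |
| Month 12 | 7 of 11 or 8 of 12 | 1 of 5 or 2 of 6 |
| Month 36 | 3 of 11 or 4 of 12 | 0 of 5 or 1 of 6 |

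In every cell but one, the lost visits include the last scheduled one. The exception is 0 of 5, where month 36 is itself the last visit.

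**5. Illustration only.** The plan specifies no five-year group mean. Suppose one were taken over continuing users. Let k of 15 subjects be non-users with missing values, let the users' mean change be D, and let the non-users' be rD. The mean over all implanted subjects is D × (1 − (1 − r)k/15), so the users' mean exceeds it by the factor 1/(1 − (1 − r)k/15).

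- r = 0 (no change): k = 1 gives 15/14 = 1.07; k = 3 gives 15/12 = 1.25.
- r = 0.5: k = 1 gives 1/(1 − 0.5/15) = 1.03; k = 3 gives 1/(1 − 1.5/15) = 1.11.
- r = 1 (same change as users): 1.00.

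Both k and r are assumed. The range shows only that the effect can be nil or material.

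**The case against.** **Section 3.1 permits exceptions.** A reader might infer that 5.2 contradicts the visit schedule. It does not: 3.1 applies unless something else is specified, and 5.2 specifies something else. This stands, and the point is a weakness of design, not an inconsistency with 3.1.

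**All testing ends.** A reader might also infer that a non-user's whole assessment battery stops. Sections 7.4 and 14.2 do not support that, because audiologic and safety testing can continue as routine care, and 10.4 plans to analyse data from all participants. It would still help to say outright that such routine results are study data.

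**Questionnaires at each appointment.** Section 5.2 also mentions questionnaires at each appointment. That sentence is about confirming device use; the later sentence sets the rule once non-use is found. If the questionnaires are meant to continue, the wording about a last set needs correcting anyway.

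**Section 10.1 does not require every measure at five years.** It fixes the endpoint time and does not say that all nine measures must be taken then in every subject. This is fair, and it is why the point is a recommended improvement and not an error. But a rule under which some enrolled subjects would lack three primary dependent measures at the endpoint time still weakens the evidence.

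**Analysis is by subject.** Section 10.5 analyses each subject individually, and a non-user still has a baseline comparison at the last set. This stands: earlier results, the last set and other subjects' own results are untouched. What is lost is the non-user's own later comparison, and 10.4 cannot supply values that were never collected.

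**Other text may cover it.** Section 14.1 offers withdrawn subjects who agree outcome and safety measurement to five years, but 5.2 says non-users are not withdrawn, and 14.1 does not say whether questionnaires are included. The study grid cited in 7.8 is in the IRB application, which is not among the documents, and it cannot be assumed to settle the matter.

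**Conclusion.** The point holds as a design weakness that should be corrected, with medium confidence, because it rests on the most natural reading of 5.2 and not on an explicit statement that questionnaires stop. On that reading an enrolled non-user has no five-year HHI, DHI or SF-36 to set against baseline, and late questionnaire summaries lean toward continuing users. That makes them too favourable only if non-users fared worse, which is plausible but not shown.

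Each non-user is 7% to 10% of the subjects and loses between 0 of 5 and 10 of 12 questionnaire visits for a last set between month 3 and month 36. A reader might take the factor of 1.25 as an estimate of bias. The documents do not support that: they state neither a non-use rate nor a group estimator, so the size of any bias cannot be given. Nor do they support a claim that the NF2 comparison is biased. An effect there would need late visits with such missing values, and its direction is unknown.

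A secondary point stands on its own. Section 14.1 refers to 5.2 as a rule for withdrawing non-adherent subjects and has withdrawn subjects replaced, while 5.2 withdraws no one for non-adherence. Whether a non-user is replaced is therefore unclear.

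**What to change.** - **5.2:** Replace the wording about a last set. Say that a subject who stops using the device remains in the study, is asked to complete HHI, DHI and SF-36 at every remaining scheduled visit to five years, and has audiologic results from routine care recorded as study data.
- **10.4 and 10.5:** Say that late-visit summaries include the observed values of all implanted subjects, and report at each visit the number using the device and the number assessed. Assigning a non-user's own pre-operative value where a later one is missing should be a sensitivity analysis only.
- **5.2 and 14.1:** Reconcile the two on whether non-adherence counts as withdrawal, and state whether a non-user is replaced.

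The cost is wording in four sections plus three questionnaires at no more than 10 visits per non-user (3 × 10 = 30 forms) if use stops at month 3 or later. These subjects are already followed to five years. Some may decline, so the numbers assessed must be shown, and the late result may be less favourable than one based on continuing users.
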